# **APPENDIX 5: MICROBIOLOGICAL ASSESSMENTS**

Two wound swabs of ulcer will be sent for aerobic and anaerobic cultures of contaminating microbes, which will be performed by a central microbiology lab, and for molecular evaluation of microflora at V1, V3, V4, V5, V6 and V7 (and/or at early termination). Suitable culture samples must be obtained via wound swab. Biopsy, curettage, and needle aspirations are not allowed. If suitable culture material is not available due to healing of the ulcer, this will be documented by the investigator. All wound swabs will be obtained BEFORE debridement.

The eradication/persistence of each baseline pathogenic species will be determined based on culture results reported by the laboratory. If a subject's culture result is missing for V7, the baseline pathogen will be presumed eradicated if a) ulcer closure is achieved, b) because of ulcer healing there is a lack of suitable tissue sample/culturable material (as documented by the investigator), or c) the culture result is otherwise missing, and pathogen eradication was achieved in the last available culture result. In all other circumstances, baseline pathogen persistence (i.e., not eradication) will be presumed.

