#### Research hypotheses

Because this trial is focused on safety, no primary research hypotheses (hypotheses tested using statistical tests) will be tested. However, two secondary endpoints will be tested statistically, one of which has to meet a priori conditions to decide validity of testing.

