  - Laboratory evaluations and vital signs assessments will be summarized by dose group (including placebo group) and time point of collection (i.e., visit number starting with randomization visit) (see shell Table 2).
    - Tables will also be constructed for each subject per timeline (see Shell Table 3)

[figure not shown]
SAP: LLA-Nu3-CLIN002 Page 8 of 21

 Table describing change in value and percentage change from baseline for each visit will be provided for vital signs for each subject (see Shell Table 4)

- Table describing out-of-normal range shifts will be provided for clinical laboratory results for each subject, grouped according to dose group (See Shell Table 5)
- Table describing changes noted in physical examinations (at each visit after randomization) will be constructed for each subject, grouped according to dose group (see Shell Table 6)
- Efficacy date will be analyzed as follows:
  - Summary statistics of DFUs that healed by treatment group by 6 weeks (numbers and percentage healed); graph showing weekly percentage of wounds healed by treatment group
  - PAR weekly plot by treatment group; summary table of PAR values by week and treatment group
  - Time to heal within 6 weeks (summary time to heal statistics by treatment group) using Kaplan-Meier method; probability of wound healing (1-survival ≡ 1-wounds not healed) plot by treatment group. If the percentage healed figures for the 5% and 10% Nu-3 groups at 6 weeks is within 10% and a statistical power calculation shows that the proportions of wounds healed for the combined versus placebo groups is at least 80%, the times to heal will be tested using the logrank test.
  - Bacterial counts (CFU/g) for weeks 0-4 will be analyzed by (a) reporting the means and standard deviations for each group at each time point and (b) using GLMM (general linear modeling with repeated measures [weeks 1-4] and counts at week 0 as a factor)
  - Microbiological data will be summarized for each of the 3 treatment groups for each visit (visits 1, 3, 4, 5, 6, 7; unscheduled visit; early termination) as follows (a) list of species detected in each microbiological sample (Shell Table 11); and (b) susceptibility testing to the following drugs for each microbiological sample: penicillin, vancomycin, and linezolid (Shell Table 12)
    - \*A reason will be given in each instance in which susceptibility testing was *not* done (e.g., no growth).

SAP: LLA-Nu3-CLIN002 Page 9 of 21

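### The SAP models bacterial counts per gram, but the protocol takes only wound swabs, and neither document defines a specimen mass, a swab area or quantitative culture

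*SAP*

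**What the plan says.** The efficacy part of the SAP's Analysis section has one quantitative microbiology outcome: "Bacterial counts (CFU/g) for weeks 0-4 will be analyzed by (a) reporting the means and standard deviations for each group at each time point". The same item adds a model: "using GLMM (general linear modeling with repeated measures [weeks 1-4] and counts at week 0 as a factor". The other microbiology items there are the species found in each sample (Shell Table 11) and susceptibility to three drugs (Shell Table 12).

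Protocol Appendix 5 describes the specimens: "Two wound swabs of ulcer will be sent for aerobic and anaerobic cultures of contaminating microbes", with molecular evaluation of microflora as the other use. It restricts how they are taken: "Suitable culture samples must be obtained via wound swab. Biopsy, curettage, and needle aspirations are not allowed". It then defines a categorical outcome: "The eradication/persistence of each baseline pathogenic species will be determined based on culture results reported by the laboratory". A rule follows for a missing Visit 7 culture, under which the pathogen is presumed eradicated if, among other cases, the ulcer has closed.

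On testing, the SAP's Research hypotheses section says that "two secondary endpoints will be tested statistically, one of which has to meet a priori conditions to decide validity of testing". It does not name the two. The only conditional test in the Analysis section is the log-rank test on time to heal, so the other is, by inference, the bacterial count model.

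**The concern.** A count per gram needs a specimen of known mass. A swab taken as these documents describe has none, and the procedures that would normally supply a weighed specimen are barred. The analyst would have to drop the analysis, supply a denominator that the plan does not give, or print swab counts under a per-gram label.

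Two things are at stake. First, this is the only modelled outcome for the secondary objective on antimicrobial effects (protocol section 4), and the protocol Synopsis has the DMC review all data after Cohort 2 before recommending a dose for the next study. Second, the basis of the count decides what it measures. A count per swab that depends on how much wound was swabbed would fall as the ulcer shrinks, so a healing difference between arms could be taken for bacterial killing.

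**Working it through.** The plan gives no figure to reproduce here, so the check is one of units, followed by a short calculation of what a mislabelled count could do.

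**Step 1. What the unit requires.** CFU/g = (colonies in the specimen) / (specimen mass in g). The plan therefore needs a quantitative culture for the numerator and a mass for the denominator.

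**Step 2. Search of both documents.**

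| Place | What it gives | Quantified culture? | Mass or swab area? |
|---|---|---|---|
| Protocol section 4 | Change in wound microbial population; culture and microflora analysis | No | No |
| Protocol section 8, visit procedures | Two swabs, one for culture and one for microflora | No | No |
| Protocol section 9, Schedule of Events | A culture swab row and a microflora swab row; no swab if the wound is closed | No | No |
| Protocol Appendix 4 | Swabs before cleansing or debridement | No | No |
| Protocol Appendix 5 | Swab-only culture at a central laboratory; eradication or persistence by species | No | No |
| SAP, Analysis | Counts named in CFU/g, no derivation | Named only | No |
| SAP, Shell Tables 11 and 12 | Species; susceptibility | No | No |

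No shell table holds a bacterial count, and no swab-to-gram conversion appears. In the other direction, the eradication outcome defined in Appendix 5 has no analysis in the SAP.

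**Step 3. Effect of wound size, if counts are per swab.** Assume that the whole wound bed is swabbed (no technique is given). Then count = density × area. With equal starting areas, and equal densities throughout, the log10 difference between arms is log10(f_active / f_placebo), where f is the fraction of baseline area remaining.

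- 50% reduction on active and none on placebo (illustrative): log10(0.50 / 1.00) = −0.30, an apparent fall with no killing.
- 50% reduction in both arms: log10(0.50 / 0.50) = 0.

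The 0.30 log10 thus applies only to a between-arm difference in area reduction of that size. Adjusting for the week 0 count does not remove it, because the areas diverge after week 0.

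**Step 4. Effect of an assumed mass.** If one mass m is applied to every swab, log10(CFU/g) = log10(count) − log10(m), and the second term cancels between arms. On the untransformed scale all counts are multiplied by 1/m, so the ratio of means is unchanged. A single assumed mass alters the reported level, not the relative comparison. Unrecorded masses that differ between swabs would add error that the week 0 adjustment does not remove.

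**The case against.** The strongest reply is that part of the method is out of sight. Appendix 5 sends culture to a central laboratory and refers to a study reference manual for obtaining, storing and shipping swabs. A swab weighed before and after sampling would give a mass, or the unit may be a simple slip. This limits the claim: a reader might infer that the quantity cannot exist in the data, and the documents do not show that. They show that neither of them defines it. The manual's stated scope does not extend to assay or units, and a slip would still leave the basis of the count unstated. The missing-culture rule in Appendix 5 does mention a tissue sample, but the same appendix bars the tissue procedures, so it supplies no mass.

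A reader might also infer a large bias from other numbers. The protocol's 2 to 10 cm² eligibility range gives log10(10/2) = 0.70 if the whole bed is swabbed, but that is spread between subjects, part of which the week 0 count would absorb. A tenfold range of assumed swab mass (0.01 g against 0.1 g, illustrative) gives 1.0 log10, but as a constant it cancels, as Step 4 shows. Neither measures bias between arms.

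Finally, this is a secondary outcome in a 32-subject pilot with no sample size calculation and no primary hypothesis test, and the species and susceptibility listings still describe the flora. That stands. It would be wrong to say that the antimicrobial objective has no analysis at all; it has only listings if the count is unusable.

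**Conclusion.** The concern holds as an inconsistency between the SAP's unit and the sampling the protocol describes. Unless an unseen laboratory method supplies a mass, the only modelled antimicrobial outcome either cannot be computed or would report swab counts under a per-gram label.

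The size of any bias cannot be fixed from the documents. Under whole-wound swabbing it ranges from zero, when area reduction is equal between arms, to 0.30 log10 for the illustrative case of 50% against none. That rests on the swabbing assumption and on equal bacterial density. The reach is one secondary objective; the primary safety analysis does not depend on it. That the count model is one of the two tested secondary endpoints is an inference from the SAP. Its General section, which says that no hypotheses will be tested, does not settle the matter.

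**What to change.** Before database lock, revise the SAP's Analysis section as follows.

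1. Replace CFU/g with the unit that the central laboratory actually reports per swab. State that the count is not normalised to wound size unless a swab area was recorded. Reporting per mL of eluate does not escape this: without a fixed area it depends on wound size in the same way.
2. Add a by-group summary of eradication or persistence of baseline pathogens at Visit 7, using the Appendix 5 rule, including presumed eradication on closure. Show observed and presumed eradication separately, since the presumption itself depends on healing.
3. If the laboratory reports only qualitative or semi-quantitative growth, replace the count model with that summary and with growth grade by group.

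The cost is an enquiry to the laboratory and SAP text; swabs and visits do not change. The downsides are that results will not be comparable with per-gram tissue counts, and per-swab counts will still depend partly on wound size. A fixed, recorded swab area would address the latter while ulcers stay large enough. It needs a protocol amendment with ethics approval and a change in site procedure, cannot be applied to swabs already taken, and is optional. Newly contracted quantitative culture would likewise be a procedural change and not clearly cheap.

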#### General

Descriptive statistical methods will be used to summarize the data from this study. These include number of subjects (n), mean and standard deviation (SD) for continuous variable data (medians and IQR [interquartile range] values will be given when the distribution of variable values is non-normal), and frequencies and percentages for categorical variable data. There will be no hypothesis testing performed. All data collected during the study will be reported and analyzed.

Unless specified otherwise, all statistical testing will be two-sided and performed using a significance (alpha) level of 0.05.

All statistical analyses will be conducted using PASW 27 (SPSS; IBM).

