#### Statistical methodology

#### Missing data

\*For calculation purposes, days to healing = date ulcer is first healed – date of randomization.

SAP: LLA-Nu3-CLIN002 Page 6 of 21

Missing data may be the result of missed visits, subjects lost to follow-up or who have died, and may be endpoint data or covariate data. Missing continuous outcome data will be imputed in this study using the LOCF (last observation carried forward). If wound healing outcomes are missing these will be imputed as follows: (a) If an event removes the index ulcer, such as an amputation, the outcome will be scored as not healed; (b) If a subject dies, the outcome will be scored as not healed; (c) If a subject is withdrawn from the study, the outcome will be scored as not healed; and (d) for all remaining non-healed index ulcers in the drug groups, the outcomes will be based on non-right-censored outcomes in the SOC group to weight outcomes.

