#### Data QC

- 1. Inspect for accuracy of input:
  - a. Plausible values
  - b. Outliers or out-of-range values
- 2. Evaluate degree and distribution of missing data; for non-endpoint data query PERI
- 3. Identify non-normal continuous variables and outliers; data for non-normal variables will include median/IQR.

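### The SAP names no scale for bacterial counts, no value for no-growth cultures and no specific rule for closed ulcers, and the natural reading is a raw-scale linear model with LOCF

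*SAP*

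**What the plan says.** The efficacy list in the SAP's Analysis section handles bacterial counts at weeks 0 to 4 in two ways: by "reporting the means and standard deviations for each group at each time point", and by "using GLMM (general linear modeling with repeated measures [weeks 1-4] and counts at week 0 as a factor". The unit is CFU/g. Neither the SAP nor the protocol gives a transformation, geometric mean, link, distribution or detection limit.

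Four other provisions touch the point.

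- **Non-normal data.** The SAP's General section says of medians and IQRs that these "values will be given when the distribution of variable values is non-normal". Data QC repeats that "data for non-normal variables will include median/IQR".
- **Missing data.** "Missing continuous outcome data will be imputed in this study using the LOCF (last observation carried forward". The causes offered are introduced by "Missing data may be the result of missed visits, subjects lost to follow-up or who have died"; ulcer closure is not among them.
- **No growth.** This appears once in the SAP, as an example of why a susceptibility test was not "done (e.g., no growth").
- **Closure.** Footnote 6 to the protocol's Schedule of Events stops swabs once the wound has closed. Protocol Appendix 5 presumes eradication of a baseline pathogen on closure, but only for the species-level outcome at Visit 7. Appendix 5 also allows swabs only, and leaves swab procedure to a study reference manual.

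**The concern.** The antimicrobial effect is a stated secondary objective (protocol section 4), and this is the only model planned for it. It also appears to be one of the two secondary endpoints that the SAP's Research hypotheses section says will be tested: the conditional one matches the logrank test, which leaves the count model as the unconditional one. That is an inference, because the section names neither endpoint.

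Bacterial counts usually spread over orders of magnitude. On the raw scale, one or two very high swabs can then dominate an arm of 8 to 12, and a real reduction can be missed. The non-normality provisions do not help, because they add summary statistics and leave the model alone.

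A closed ulcer has no count because the outcome was good. Carrying its last open-wound count forward, dropping it, or setting it to a low value gives different answers. If this is not settled in advance, the choice will be made with the data in view.

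The week-0 wording adds to this. Taken literally, a categorical factor with a distinct value for each of 32 subjects would use 32 levels and leave 32 − 32 = 0 between-subject degrees of freedom for treatment.

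**Working it through.** The plan states no SD, effect size, power or detection limit for counts, so there is no figure to reproduce. The inputs it does give are two cohorts of 12 active and 4 placebo, so 2 × (12 + 4) = 32, analysed as 12/12/8, with two-sided alpha 0.05. Everything else below is an assumption.

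**1. Skewness on the raw scale.** For lognormal counts, mean/median = exp[(SD × ln 10)² / 2].

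- SD 0.5: exp(1.151² / 2) = 1.9
- SD 1.0: exp(2.303² / 2) = 14
- SD 1.5: exp(3.454² / 2) = 389

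The largest of 8 placebo counts at one visit makes up a median 37%, 59% and 74% of the arm's total at these SDs.

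**2. Power with almost no non-detects.** Assumed: log10 mean 5, floor 10^1, within-subject correlation 0.5, a 1-log10 reduction in both Nu-3 arms and no closures. The test is ANCOVA on each subject's mean over weeks 1 to 4, with the week-0 count continuous on the same scale. The three-group test has 2 and 28 df; pooled active versus placebo has 1 and 29 df.

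| log10 SD | 2-df, raw vs log10 | Pooled, raw vs log10 |
|---|---|---|
| 0.5 | 99 vs 100% | >99 vs 100% |
| 1.0 | 45 vs 92% | 66 vs 97% |
| 1.5 | 13 vs about 60% | 30 vs 72% |

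With no true effect the raw analysis rejects 1.6 to 3.7% (2-df) and 3.8 to 4.3% (pooled), and log10 about 5%. The raw test is conservative.

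**3. The same test with no-growth samples.** Table 2 hardly tests the missing non-detect rule: at mean 10^5 and SD 1.5, placebo counts reach 10^1 in fewer than 0.5% of samples. Now assume 20% no-growth in every arm, independent of treatment, set at 10^1 (2-df test).

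| log10 SD | raw | log10 |
|---|---|---|
| 0.5 | about 97% | about 60% |
| 0.75 | about 74% | about 53% |
| 1.0 | roughly equal | roughly equal |

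Log10 is still ahead at SD 1.5. If the drug itself produces no-growth (30% active, 10% placebo), log10 is ahead from SD 0.75 upwards. The low substituted value adds large log-scale noise when no-growth is unrelated to treatment, and carries signal when it is related.

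**4. Closed ulcers.** Assume placebo open-wound log10 mean 5, limit 10^1, and closure by week 4 of 25% active and 12.5% placebo, spread evenly over weeks 1 to 4. The figures are week-4 differences, placebo minus active, in log10.

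Equal open-wound counts:

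- LOCF: 5 − 5 = 0.00
- Closed at the limit: (0.25 − 0.125) × (5 − 1) = 0.50

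True 1-log10 open-wound effect:

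- Open ulcers only: 5 − 4 = 1.00
- Closed at the limit: (0.875 × 5 + 0.125 × 1) − (0.75 × 4 + 0.25 × 1) = 4.50 − 3.25 = 1.25
- LOCF: ulcers closed at week 1 carry the untreated week-0 count, so the active mean is 4 + 0.25 × ¼ × 1 = 4.06 and the difference is 0.94

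The unstated choice therefore moves the estimate from 0.94 to 1.25 in one case and from 0.00 to 0.50 in the other.

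**The case against.** The strongest reply is that the SAP is silent on scale and does not choose the raw one, and that GLMM commonly means a generalized mixed model, which could carry a log link. Part of this stands: a reader might infer that the SAP prescribes arithmetic means of raw counts, and it does not say so. But its own expansion of the abbreviation is a general linear model, and no link or distribution follows.

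A reader might also infer that log10 analysis is always more powerful. Step 3 shows that it is not: substituting a low limit for no-growth can cost more power than the raw scale does. This stands, and it shapes the fix.

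A third tempting reading is that the plan has no rule at all for closed ulcers, or alternatively that it prescribes LOCF for them. Neither is supported. The LOCF rule may apply by default, but its list of causes omits closure and need not be exhaustive. The Visit 7 eradication rule concerns a different outcome and assigns no count.

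The unit is a fair further objection. With swabs only and no sample weight described, the documents do not show how CFU per gram is obtained. The study reference manual, not available here, may explain this and may state a detection limit. It would still not replace an analysis rule: protocol section 12.3 assigns procedures for missing data to the SAP.

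Finally, this is a 32-subject safety pilot with no sample-size calculation, so power on a secondary endpoint deserves limited weight. That affects the grade, not the omission.

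**Conclusion.** The concern holds as a gap in specification with a better method at hand. The scale, the value for no-growth cultures and the treatment of closed ulcers are all unstated, and the literal reading (raw scale, LOCF into healed ulcers) is a poor one. Confidence in the omission is high.

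The size is illustrative, since it depends on SDs, a detection limit and no-growth rates that the documents do not give. With almost no non-detects, the raw-scale loss is negligible at log10 SD 0.5 and large from SD 1.0. With 20% treatment-unrelated no-growth set at 10^1, the ranking reverses at SD 0.5 to 0.75. The raw test did not inflate false positives in these simulations, so the cost is lost power and a mean that a few swabs can dominate. It should be fixed before unblinding.

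**What to change.** Amend the SAP as follows.

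1. Model log10 counts in a repeated-measures mixed model with treatment, week, treatment-by-week and log10 week-0 count as a continuous covariate, and report geometric means. If a generalized model is intended, name its distribution and link.
2. Treat non-detects as left-censored at the laboratory's limit, or substitute a pre-stated value with a sensitivity analysis over that value. Report the proportion with no growth by arm.
3. Do not apply LOCF to closed-ulcer visits. Report open, swabbed ulcers and, as a sensitivity analysis, closed ulcers at the detection limit. Name the main analysis before unblinding: the first conditions on the ulcer staying open, and the second mixes healing with antimicrobial effect.
4. Confirm how CFU/g is derived from swabs, and correct the unit if needed.
5. Separately, reconcile the General section's "There will be no hypothesis testing performed" with the Research hypotheses section, and name the tested endpoints and the contrast (each dose versus placebo, or pooled).

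The cost is SAP wording, a little programming and one extra analysis. Results would read as ratios of geometric means. No additional data should be needed, provided that quantitative counts and a detection limit are already reported by the laboratory, which item 4 would establish.

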#### Randomization:

Randomization will be conducted to a ratio of 3:1 (active: placebo). All qualified subjects will be enrolled and randomized in two sequential Cohorts of 16 each, Cohort 1 to either Nu-3 gel at 5% or to placebo gel, and Cohort 2 to either 10% Nu-3 gel or to placebo gel. The two cohorts will be enrolled sequentially, each with 12 active and 4 placebo subjects, and safety will be evaluated by the independent Data Monitoring Committee (DMC) before proceeding to the next Cohort. At the completion of Cohort 2, the DMC will review all data and make a recommendation as to the appropriate dose for the next study.

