#### **Sample Size Calculations**

Since this is a pilot study focusing primarily on safety, no sample size calculations will be done. Based on general experience with phase 2a trials, it is planned to enroll 32 subjects (24 active and 8 placebo).

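### Entering the week-0 bacterial count as a factor, if run as a categorical term, can alias or badly weaken the treatment comparison; it should be a continuous covariate.

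*SAP*

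**What the plan says.** The SAP's Analysis section gives bacterial counts two treatments. The first is descriptive: "Bacterial counts (CFU/g) for weeks 0-4 will be analyzed by (a) reporting the means and standard deviations for each group at each time point". The second is a model, labelled GLMM and spelled out as "general linear modeling with repeated measures [weeks 1-4] and counts at week 0 as a factor". The text does not say what the levels of that factor would be, which scale is analysed, what covariance structure is used, or which other terms are fitted. Treatment group and treatment-by-week are not written down as model terms.

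The SAP's Research hypotheses section says that "two secondary endpoints will be tested statistically" and that one of them depends on conditions set in advance. The two are not named there. In the Analysis section the log-rank test of time to heal carries such conditions and the bacterial-count model carries none, so I read the bacterial-count model as the unconditional one. The SAP's General section says that, unless specified otherwise, "all statistical testing will be two-sided and performed using a significance (alpha) level of 0.05".

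The Protocol synopsis (Randomization) plans two cohorts, "each with 12 active and 4 placebo subjects". The SAP handles the microbiology in three groups: "Microbiological data will be summarized for each of the 3 treatment groups for each visit".

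**The concern.** A week-0 count is a continuous baseline measured once per subject. As a covariate it costs one degree of freedom (df). As a factor it costs one parameter for every distinct value beyond the first. If nearly every subject has a different count, the factor amounts to a subject identifier. Treatment is also constant within a subject, so nothing is left for the treatment main effect to explain.

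The SAP's Missing data section uses the term covariate, so that vocabulary was available, yet the week-0 count is called a factor. An analyst who follows the text literally would put it in the categorical role.

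At stake is the one efficacy test that appears to run without a precondition. It serves a stated secondary objective, the antimicrobial effect on wound flora. If the problem is noticed only when the model fails, the baseline term will be redefined with unblinded data in view, and the model becomes a post hoc choice.

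**Working it through.** The documents state no df, power or effect size for this model, so there is no figure of theirs to reproduce. The check counts df under each reading.

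**Inputs.** Subjects: 12 on 5%, 12 on 10%, and 4 + 4 = 8 on placebo, so N = 32 (Protocol synopsis, Randomization; SAP, Sample Size Calculations). Three groups give 3 − 1 = 2 treatment df. The response is at weeks 1 to 4 (SAP, Analysis). Complete data are assumed. The Schedule of Events drops the swab once a wound has closed, so the observed data may be fewer. The number of tied week-0 values is not given and is varied below.

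**Formulas.** With B the baseline columns and T the treatment columns:
- treatment df = rank[1, B, T] − rank[1, B]
- between-subject residual df = 32 − rank[1, B, T]

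**Continuous covariate.** rank[1, B] = 2 and rank[1, B, T] = 4. Treatment df = 4 − 2 = 2; residual df = 32 − 4 = 28.

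**Factor, all 32 counts distinct.** rank[1, B] = 1 + 31 = 32, and adding T leaves it at 32. Treatment df = 0; residual df = 0.

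**Factor with ties.** With L distinct values, rank[1, B] = L. If both treatment df are estimable, residual df = 32 − (L + 2) = 30 − L. Each level was used at least once, the remaining subjects were spread at random over the levels, and levels were assigned to arms at random 2,000 times.

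| Distinct values L | Residual df if both treatment df estimable (30 − L) | Share of assignments with both estimable |
|---|---|---|
| 16 | 14 | 100% |
| 24 | 6 | about 98% |
| 28 | 2 | about 75% |
| 30 | 0 (no error term) | about 31% |

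**Ties only at a shared no-growth value.** If k subjects share one value and the rest are distinct, L = 33 − k and residual df = 30 − (33 − k) = k − 3. A 2-df test therefore needs k of at least 4, with all three arms among the k tied subjects. Over 4,000 random assignments:

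| k | Residual df | Share in which the 2-df treatment effect is testable |
|---|---|---|
| 2 or 3 | none | 0% |
| 4 | 1 | 46% |
| 6 | 3 | 77% |
| 8 | 5 | 90% |

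Exact check at k = 4: [C(12,2)·12·8 + 12·C(12,2)·8 + 12·12·C(8,2)] / C(32,4) = (6,336 + 6,336 + 4,032) / 35,960 = 16,704 / 35,960 = 0.465.

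In this pattern every subject with a unique count has a private parameter, so the treatment main effect is estimated only from subjects with no growth at week 0.

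**All four weeks together, all counts distinct.** There are 32 × 4 = 128 records. With baseline as a main effect only, the intercept, baseline and week use 1 + 31 + 3 = 35. Treatment adds 0. Treatment-by-week adds 2 × 3 = 6, leaving 128 − 41 = 87 residual df. If baseline-by-week is also fitted (31 × 3 = 93 more), the rank is 35 + 93 = 128 and treatment-by-week has 0 df too.

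**The case against.** The strongest reply is that one loosely used word is being read as a technical commitment. The SAP never says that each distinct count is a level. The same bullet summarises the counts by means and SDs, and it expands GLMM as a general linear model, so its terminology is informal. Read as ordinary baseline adjustment, the model keeps 28 residual df and the problem disappears. This stands as a limit on certainty. It does not settle the matter, because the SAP does not say which reading applies and the other terms are unlisted under both.

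A reader might infer that the model necessarily leaves no df and cannot return any treatment effect. The documents do not support that. Zero df requires all counts to be distinct. The ulcers are clinically noninfected and the SAP foresees samples without growth, so shared values are plausible. Treatment-by-week can also survive. That interaction, however, asks only whether group differences change over weeks 1 to 4. A reduction reached by week 1 and held constant would not show in it.

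A reader might also infer that treatment was left out of the model. The neighbouring summaries are by group, so incomplete specification is the fairer reading.

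It is also true that complete aliasing would be visible in the output and that the group means and SDs would be reported regardless. Partial aliasing is less obvious: an estimate would appear, but it would rest on a subset of subjects and few residual df.

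**Conclusion.** The concern holds conditionally. If the week-0 count is run as a categorical term and all 32 values differ, the treatment main effect has 0 df and the between-subject residual is 0, against 2 and 28 with a continuous covariate. If values are nearly all distinct, the full treatment effect is mostly untestable. With more ties it becomes estimable, usually at a real cost: about 6 residual df with 24 distinct values and 14 with 16.

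This rests on three assumptions: the literal reading of factor, complete data in 32 subjects, and a number of ties that the documents do not give. It does not show that the analysis is bound to fail. It shows that the term as written gives a weaker or unusable comparison, and that a better term is available at no cost.

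The primary endpoint analysis is a descriptive summary of treatment-emergent adverse events and is untouched. This is a correction to a secondary microbiological analysis in a safety pilot, worth making before unblinding but not a threat to the trial's main purpose.

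**What to change.** In the SAP's Analysis section, replace the factor wording so that the week-0 count enters as a continuous covariate, on the same stated scale as the response (for example log10 CFU/g). If a log scale is chosen, say how a no-growth result is entered, because the log of zero is undefined.

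List the fixed effects: treatment group (5%, 10%, placebo), week (1 to 4) and treatment-by-week. Report each dose-minus-placebo difference, at a week or weeks named in advance, with a 95% confidence interval.

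The cost is a sentence or two of SAP text. No extra data, visits or subjects are needed.
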